### **2.4.6.2 Compliance**

Compliance to the treatment regimen will be monitored in terms of the percentage of scheduled infusions the patient receives during the treatment period, including exposure from the original study. A patient is considered noncompliant if the patient missed 4 or more infusions (excluding for-cause missed infusions, such as when the missed infusions are required by the protocol due to a dose limiting toxicity) every 12-month period in the extension study. Whether a missed infusion is for-cause or not will be reviewed and determined by the clinical team; the decision will be used in the analysis of compliance.

Overall Compliance =  $100\% \times \text{Total number of infusions received} / \text{Total number of expected infusions}$

where total number of expected infusions refers to the number of infusions expected between the first infusion in this study and the date of withdrawal or date of completion. It is calculated as the integer part of (Date of withdrawal/completion – Date of the first infusion in the extension study)/14. For interim calculations, date of withdrawal/completion will be substituted by the date of the database extraction used.

Compliance excluding for-cause =  $100\% \times \text{Total number of infusions received} / (\text{Total number of expected infusions} - \text{total number of for-cause missed infusion})$

where the denominator is calculated as the integer part of [(Date of withdrawal/completion – Date of the first infusion in the extension study)/14] – number of for-cause missed infusions. For interim calculations, date of withdrawal/completion will be substituted by the date of the database extraction used.

Overall compliance and compliance excluding for-cause will be summarized descriptively as quantitative variable using safety population. The numbers and percentages of patients whose compliance are <80%, >=80% to <90%, >=90% to <100% and >=100% will be provided. Number and percentage of patients will be presented for missing 4 or more scheduled infusions, by every 12 months of treatment exposure.

Any interruption during infusion will be captured and provided in data listing. Any irregularities in dosing (such as dose change or dose interruption) due to an AE will be captured with AE details, and will be provided with AE reports.

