### ***Protocol deviations***

During the review of the database, compliance with the protocol will be examined with regard to inclusion and exclusion criteria, treatment, prohibited therapies, and timing and availability of planned assessments. Protocol deviations will be identified by the study team before database lock and classified as minor, major or critical deviations, in consideration of whether this could potentially affect efficacy assessment endpoints. A listing of major or critical protocol deviations for all treated patients will be produced.

In addition to the above, the two conditions listed below will be evaluated:

**Noncompliance:** Missing 4 or more infusions for each 12 month period in this study, excluding for-cause missed infusions (such as when the missed infusions are required by the protocol due to a dose limiting toxicity), calculated over the extension phase only. Whether a missed infusion is for-cause or not will be reviewed and determined by the clinical team; the decision will be used in the determination of noncompliance. For details of calculations, please refer to [Section 2.4.6.2](#).

**Prohibited medications intake:** The prohibited medications in this study have been defined in [Section 2.1.2](#). The prohibited medication use that could potentially modify the effect of olipudase alfa (which includes, but not limited to, certain antidepressant) or could threaten the safety of olipudase alfa are major protocol deviations.

The protocol deviations identified by the review of the above two conditions will be listed for all treated patients as protocol deviations.

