## **2.4.6 Extent of investigational medicinal product exposure and compliance**

### **2.4.6.1 Extent of investigational medicinal product exposure**

The extent of study treatment exposure will be assessed from the first infusion in the original study, and will be summarized using safety population. The duration of exposure is defined as the number of weeks between first infusion in the original study and disposition date in the study: (disposition date of the study [or the cutoff date for database lock if the patients are still ongoing] – first infusion date from original study + 1)/7. The number of infusions received and the duration of exposure will be summarized using safety population.

The distribution of weeks on study treatment (<12 weeks, >=12 weeks to <26 weeks, >=26 weeks to <38 weeks, >=38 weeks to <52 weeks, >=52 weeks to <64 weeks, etc) will be provided using number and percentage of patients by age group cohorts and overall. The total number of patient-years of exposure will also be provided.

Any overdose will be captured as an AE, and will be reported as such.

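### SAP 2.4.6.2 leaves the compliance period contradictory, miscounts expected infusions by one depending on the end date, and does not reconcile its noncompliance rule with protocol 8.5.1

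*SAP*

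**What the plan says.** SAP 2.4.6.2 opens by defining compliance as "the percentage of scheduled infusions the patient receives during the treatment period, including exposure from the original study". SAP 1.5 likewise moves the start of the treatment period back to the first infusion in the original study. For exposure, SAP 2.4.6.1 states: "The extent of study treatment exposure will be assessed from the first infusion in the original study".

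The formulas that follow use another period. In SAP 2.4.6.2, "total number of expected infusions refers to the number of infusions expected between the first infusion in this study and the date of withdrawal" or completion. The count is the integer part of the days between those dates divided by 14. The numerator, infusions received, has no period. "For interim calculations, date of withdrawal/completion will be substituted by the date of the database extraction used". The version that excludes for-cause misses uses the same base. Results are banded: "The numbers and percentages of patients whose compliance are <80%, >=80% to <90%, >=90% to <100% and >=100% will be provided".

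SAP 2.2 describes noncompliance as "Missing 4 or more infusions for each 12 month period in this study, excluding for-cause missed infusions", and says that it is "calculated over the extension phase only". It then sends the reader to 2.4.6.2 ("For details of calculations, please refer to" that section). Protocol 8.5.1 has a different rule: two infusions missed in a row, or four in total, in each 12-month period. It makes no exception for for-cause misses.

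**The concern.** There are three separate faults.

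- **Period.** The opening sentence of 2.4.6.2 and its formulas cannot both be right, and the numerator could be programmed either way.
- **Count.** Dividing days by 14 and dropping the remainder counts completed intervals. The infusion on day 0 is received but never expected. Whether this shows in the result depends on how long after the last dose the end date falls, and the SAP does not tie completion to any particular date.
- **Noncompliance rule.** The SAP drops the consecutive-miss criterion and adds a for-cause exclusion. Neither change is listed in SAP 1.5 or 1.6.

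At stake is the band in which a patient is reported, and who appears in the deviation listing. Interim use is a real case: SAP sections 3 and 4 foresee interim reports and database locks, and 2.4.6.2 gives its own rule for them.

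**Working it through.** The plan states no compliance figure, so there is nothing to reproduce. I put schedules through its formula.

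**Inputs**
- Dosing interval 14 days, window ±3 days (protocol 8.1.1).
- Expected E = integer part of (end date − first extension infusion date)/14 (SAP 2.4.6.2).
- Numerator taken as extension-only, following SAP 2.2.
- End date: the extraction date at an interim cut. The end-of-treatment visit is 14 ± 7 days, and the safety call 30 to 37 days, after the last administered dose (protocol 6.1.2).

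**Step 1: general result on an exact 14-day schedule.** Let the last scheduled dose fall on day 14k and the end date d days later. Infusions scheduled, counting day 0, are k + 1. The SAP gives E = k + int(d/14). The error is therefore int(d/14) − 1: one too low for d = 0–13, zero for d = 14–27, one too high for d = 28–41.

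**Step 2: interim cut, infusions entered to date.** At 365, 1095 and 3285 days, E = 26, 78 and 234. Infusions scheduled are 27, 79 and 235. A fully adherent patient shows 27/26 = 103.8%, 79/78 = 101.3% and 235/234 = 100.4%.

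At 1 year:

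| Missed | SAP result | True result | Band, SAP | Band, true |
|---|---|---|---|---|
| 1 | 26/26 = 100% | 26/27 = 96.3% | ≥100% | 90 to <100% |
| 3 | 24/26 = 92.3% | 24/27 = 88.9% | 90 to <100% | 80 to <90% |
| 6 | 21/26 = 80.8% | 21/27 = 77.8% | 80 to <90% | <80% |

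At 3 years one miss shows 78/78 = 100% (true 78/79 = 98.7%). At 9 years it shows 234/234 = 100% (true 234/235 = 99.6%).

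**Step 3: final analysis.** Take 27 infusions, all received, the last on day 364. If completion is the end-of-treatment visit, a visit 7–13 days after the last dose gives 27/26 = 103.8%, and one at 14–21 days gives 27/27 = 100%. If completion is the safety call, the result is 27/28 = 96.4%. On that last basis two misses show 25/28 = 89.3% (true 25/27 = 92.6%), and five show 22/28 = 78.6% (true 22/27 = 81.5%).

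**Step 4: why adding 1 is not enough.** The flow-chart notes in protocol Section 1 date the visit schedule from the first infusion of the previous study. If the first extension infusion is given 3 days late, the planned infusion 26 intervals on is 26 × 14 − 3 = 361 days away. Then int(361/14) + 1 = 26, although 27 were due. Rounding to the nearest integer instead gives 26 + 1 = 27.

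**Step 5: the two noncompliance rules.** A patient whose only misses in a 12-month period are two in a row is noncompliant under protocol 8.5.1 but not under the SAP rule (2 < 4). Four for-cause misses in a period count under the protocol and not under the SAP.

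**The case against.** - **The period is settled elsewhere.** SAP 2.2 says extension only and points to 2.4.6.2, and the denominators there are explicit. This makes extension-only the favoured reading. It also makes the opening sentence of 2.4.6.2 wrong, so the text still needs correcting.
- **The count is often right.** At the nominal end-of-treatment visit, 14 days after the last dose, the error is zero. At an interim cut, an infusion not yet entered offsets the missing day-0 infusion. The ±3-day window also blurs the day limits in Step 1. All of this stands. The formula is right for some end dates and wrong for others, and the SAP does not fix which applies.
- **Protocol 8.5.1 is operational.** It prompts a discussion with the medical monitor and prescribes no analysis. The SAP explains its for-cause exclusion in 2.2 and 2.4.6.2, and the general deviation review in 2.2 could still find consecutive misses. This too stands. What remains is that the explicit rule omits one criterion without saying so, and that SAP 1.5 lists neither difference.

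A reader might infer that the numerator spans both studies, so that reported compliance would run far above 100%. The documents do not support that: SAP 2.2 points the other way, and sizing it would need original-study infusion counts that neither document gives. Nor is the expected count always one short, as Step 1 shows.

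**Conclusion.** The point holds and is minor. The period is contradictory as written. With an extension-only numerator, expected infusions can be wrong by one in either direction. For a fully adherent patient at an interim cut, the overstatement is 3.8 points at 1 year, 1.3 at 3 years and 0.4 at 9 years. If the safety call is taken as completion, the 1-year result is understated by 3.6 points. Patients near a cut-point change band, and the top band can hold both perfect attendance and one miss.

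This rests on a schedule close to 14 days and, for the interim figures, on infusions being entered up to the extraction date. Only the descriptive compliance tables and the deviation listing are affected. No analysis population and no inferential result depends on them. I take no view on which noncompliance rule is right; the two must be reconciled.

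**What to change.** - State one period for numerator and denominator. Extension-only matches SAP 2.2 and the existing formula. Correct the opening sentence of 2.4.6.2 to agree.
- Define expected infusions as the number of planned 2-weekly infusions, including the first extension infusion, with planned dates counted from the actual date of that infusion. Equivalently, take days between first and last planned infusion divided by 14, rounded to the nearest integer, plus 1.
- End the count at the last planned infusion due on or before the data cutoff for ongoing patients. For others, end it at the last one due on or before the documented decision to stop treatment or completion of the treatment period. Doses missed before withdrawal then count, and the end-of-treatment visit and safety call do not.
- Use the same base, minus for-cause misses, for the version that excludes them.
- Reconcile the noncompliance rule with protocol 8.5.1. Either add the two-consecutive criterion to the deviation check, or list its omission and the for-cause exclusion as departures in SAP 1.5.

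The cost is SAP wording and one corrected formula, with no new data. The deviation listing may gain patients if the consecutive criterion is added.

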#### **2.4.7 Analyses of safety data**

The safety results will be presented using the safety population. Unless specified otherwise, the displays will include the original study data along with data collected in this study. Patients will be summarized and displayed by original study identifier, age cohort and overall. Safety data will be reported up to and including the time of treatment withdrawal, and follow-up for AEs, where applicable. The baseline value is the last available value before the first infusion of olipudase alfa in the original study, except for hematology parameters and possibly ECG parameters. For complete definition of baseline, refer to [Section 2.6.1](#).

For all safety data, the observation period in this study is the **on-treatment period**, which is defined as the time from the first infusion of IMP (included) from original study to the end of the current study

The following definitions regarding potentially clinically significant abnormality (PCSA) will be applied to laboratory parameters, vital signs and ECG:

- The PCSA values are defined as abnormal values considered medically important by the sponsor according to predefined criteria/thresholds based on literature review and defined by the sponsor for clinical laboratory tests, vital signs, and ECG. These values are provided in [Appendix A](#).
- PCSA criteria will determine which patients had at least 1 PCSA taking into account all evaluations performed, including unscheduled or repeated evaluations.
- Before determining a value as PCSA, the value will be rounded to the precision that the PCSA criterion is defined.

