4 INTRODUCTION AND RATIONALE

4.1 INTRODUCTION

Human acid sphingomyelinase deficiency (ASMD) is a serious, rare, life threatening lysosomal storage disorder for which only palliative treatment exists. Patients with ASMD are unable to metabolize sphingomyelin properly due to mutations in SMPD1, the gene encoding acid sphingomyelinase (ASM), whose transcription and translation results in a defective (ASM) enzyme. Inactivity of ASM leads to the lysosomal accumulation of sphingomyelin and, secondarily, increases in cholesterol and other related lipids, mostly in the organs, such as the spleen, liver, lung, and bone marrow.

Historically, ASMD has been diagnosed as Niemann-Pick Disease (NPD) and of either Type A or Type B disease. Type A (NPD A) is characterized as the early-onset and acute neuropathic form of (NPD) and results in failure to thrive, hepatosplenomegaly, rapidly progressive neurological degeneration, and death, usually before the age of 3 years (1). Niemann-Pick disease Type B (NPD B) is a milder disease with little or no neurological involvement that may already have manifestations in childhood. The most common disease manifestation is hepatosplenomegaly. Other more variable features include liver dysfunction, pulmonary disease, retinal stigmata, and growth retardation. Niemann-Pick disease Type B is usually diagnosed in childhood after organomegaly is observed, typically after the age of 2 years. Most patients diagnosed with Type B disease live into adulthood. Being an autosomal recessive single gene disease, ASMD is acknowledged to generate a spectrum of phenotypes. Accordingly, cases classified as intermediate to the A and B extremes have been reported. Patients with this intermediate form (NPD A/B) may develop neurologic symptoms during childhood and have a chronic neurodegenerative disease course.

Sanofi Genzyme is developing a potential enzyme replacement therapy for ASMD with olipudase alfa, a recombinant human acid sphingomyelinase, for the treatment of the non-neurological manifestations of ASMD. This recombinantly-derived enzyme is expressed in Chinese hamster ovarian cells transfected with olipudase alfa complementary DNA that encodes a 627-residue peptide chain. The resulting gene product retains the enzymatic activity and lysosomal targeting of the native protein.

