9.2.4 Hematology

Hemoglobin and platelet counts will be assessed as safety and as efficacy parameters, as ASMD results in hematologic disorders. An additional blood sample will be obtained for hemoglobin and platelet count at least 24 hours and up to 2 weeks apart from the sample collected for clinical laboratory tests at the time points specified in [Section 1.1](#) through [Section 1.5](#).

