11.6.3 Analyses of safety data

Safety assessments are described in [Section 9.1.4](#) through [Section 9.1.15](#). All safety analyses will be performed on the safety set (defined in [Section 11.4](#)). No formal inferential testing will be performed. Summaries will be descriptive in nature.

The following definitions will be applied to laboratory parameters, ECGs, and vital sign measurements.

- The potentially clinically significant abnormality (PCSA) values are defined as abnormal values considered medically important by the sponsor according to predefined criteria/thresholds based on literature review and defined by the sponsor for clinical laboratory tests and vital signs.
- PCSA criteria will determine which patients had at least 1 PCSA during the treatment period, taking into account all evaluations performed during the treatment period, including unscheduled or repeated evaluations. The number of all such patients will be the numerator for the treatment PCSA percentage.
- Treatment period: the treatment period used for quantitative analysis is defined as the time from first dose to the last dose of IMP +14 Days.

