#### **2.4.7.2 Clinical laboratory evaluations**

For parameters that are reported as BQL (below the quantification limit), the results often convey a clinically meaningful change. Therefore, a numerical value is necessary to be imputed for including these in descriptive statistics calculations as well as plotting them in by-patient graphs. For all these parameters the lower limit of quantification (LLOQ) is available in the database. The imputed value for BQL will observe the same precision as reported values, but will be lower than the LLOQ by the minimum of that precision. For example, if a parameter is reported to two decimal places, and its LLOQ is X, then the imputed value of BLQ is (X-0.01). On the other hand, if a parameter is reported to one decimal place, and its LLOQ is X, then the imputed value of BLQ is (X-0.1). Listing will provide data as BQL and <LLOQ where LLOQ will be populated.

Observed values, change from baseline and percent change from baseline to scheduled study time points will be summarized in separate groups of hematology (excluding hemoglobin and platelets which are considered efficacy parameter, hence the analyses have been described in [Section 2.4.8.7](#)), liver function tests, lipids, coagulation, etc. as described in [Section 2.1.3.3](#). By patient plots of WBC, ALT, AST, total bilirubin will be provided. Summary plots over time will also be provided as needed.

Laboratory values will be classified as normal, above normal, or below normal based on normal ranges when provided by the laboratory. Shifts from baseline to scheduled time points, any time during the on-treatment period and the last available value, in the abnormality of any parameters will be provided.

PCSA values for hematology and liver function tests (provided in [Appendix A](#)) during the study (from first infusion in the original study to last available observation) will be summarized. PCSA values for hematology, liver function test and clinical chemistry parameters will be provided in separate listings.

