## Appendix A Potentially clinically significant abnormalities (PCSA) criteria

Measures	Adult criteria	Pediatric criteria
Liver function tests		
ALT	>3 * ULN >5 * ULN >10 * ULN >20 * ULN	Same as adult
AST	>3 * ULN >5 * ULN >10 * ULN >20 * ULN	Same as adult
Alkaline Phosphatase	>1.5 * ULN	Same as adult
Total Bilirubin	>1.5 * ULN >2 * ULN	≥1.3 ULN
ALT and Total Bilirubin	ALT >3 * ULN and Total Bilirubin >2 * ULN	Same as adult
Hematology		
WBC	<3.0 GIGA/L (non-Black), <2.0 GIGA/L (Black), ≥16.0 GIGA/L	12 years or above, but less than 18 years by age: <4.5 GIGA/L >13.5 GIGA/L 6 years or above, but less than 12 years by age: <5.0 GIGA/L >17.0 GIGA/L 2 years or above, but less than 6 years by age: <3.0 GIGA/L >16.0 GIGA/L 28 days/1 month to 23 months old <4.0 GIGA/L >20.0 GIGA/L

Measures	Adult criteria	Pediatric criteria
Lymphocytes	>4.0 GIGA/L	12 years or above, but less than 18 years by age: <0.6 GIGA/L >6.0 GIGA/L 6 years or above, but less than 12 years by age: <1.0 GIGA/L >8.0 GIGA/L 2 years or above, but less than 6 years by age: <1.0 GIGA/L >9.5 GIGA/L 28 days/1 month to 23 months old <2.0 GIGA/L >13.5 GIGA/L
Neutrophils	<1.5 GIGA/L (non-Black) <1.0 GIGA/L (Black)	2 years or above, but less than 18 years by age: <1.2 GIGA/L >1.0 ULN 28 days/1 month to 23 months old <1.0 GIGA/L (1-3 months) <1.2 GIGA/L (3-24 months) >1 ULN
Monocytes	>0.7 GIGA/L	N/A
Basophils	>0.1 GIGA/L	N/A
Eosinophils	>0.5 GIGA/L or >ULN if ULN $\geq$ 0.5 GIGA /L	Same as adult
Hemoglobin	Males: $\leq$ 115 g/L ( $\leq$ 7.14 mmol/L) and 20% decrease from baseline; $\geq$ 185 g/L ( $\geq$ 11.48 mmol/L) Females: $\leq$ 95 g/L ( $\leq$ 5.9 mmol/L) and 20% decrease from baseline; $\geq$ 165 g/L ( $\geq$ 10.24 mmol/L) Decrease from Baseline $\geq$ 20 g/L (1.24 mmol/L)	24 months/2 years to $<$ 16/18 years old: <10.0 g/dL and 20% decrease from baseline, or decrease from baseline $\geq$ 2 g/dL 28 days/1 month to 23 months old (Infants): <9.0 g/dL and 20% decrease from baseline, or decrease from baseline $\geq$ 2 g/dL
Hematocrit	Males: $\leq$ 0.37 v/v and 20% decrease from baseline; $\geq$ 0.55 v/v Females: $\leq$ 0.32 v/v and 20% decrease from baseline; $\geq$ 0.5 v/v	2 years or above, but less than 18 years by age: <0.32 l/l or 32% 28 days/1 month to 23 months old <0.29 l/l or 29% >0.42 l/l or 42%
RBC	18 years or above by age $\geq$ 6 TERA/L	N/A
Platelets	<100 GIGA/L and 20% decrease from baseline $\geq$ 700 GIGA/L	Same as adult

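### PCSA counts for liver tests and other absolute-limit criteria are not split by baseline status, so abnormalities present before treatment enter the on-treatment percentage

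*SAP*

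**What the plan says.** SAP 2.4.7 sets the counting rule: "PCSA criteria will determine which patients had at least 1 PCSA taking into account all evaluations performed, including unscheduled or repeated evaluations". SAP 2.4.7.2 gives the window for hematology and liver tests: "from first infusion in the original study to last available observation) will be summarized". Protocol 11.6.3 describes the same kind of count and says what it is for: "The number of all such patients will be the numerator for the treatment PCSA percentage". Neither document divides this count by whether the patient already met the limit before treatment.

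The limits are in SAP Appendix A and are of two kinds.

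- **Absolute.** All the liver rows are plain multiples of the upper limit of normal (ULN), for example "ALT >3 * ULN and Total Bilirubin >2 * ULN". WBC, lymphocytes, neutrophils, eosinophils and pediatric hematocrit are also absolute, as are monocytes and basophils in adults.
- **Relative to baseline.** Low platelets are "<100 GIGA/L and 20% decrease from baseline", with children on the same rule. Low hemoglobin in children aged 2 years and over is "<10.0 g/dL and 20% decrease from baseline, or decrease from baseline" of at least 2 g/dL. Adult and infant low hemoglobin and adult low hematocrit also require a fall.

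On the disease itself, Protocol 4.1 says: "Other more variable features include liver dysfunction, pulmonary disease, retinal stigmata, and growth retardation". Protocol 9.2.4 says: "Hemoglobin and platelet counts will be assessed as safety and as efficacy parameters, as ASMD results in hematologic disorders".

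**The concern.** Baseline in this study is the value before the first dose in the parent study, so the plan already holds what it needs to tell a new abnormality from an old one. For the absolute-limit criteria the PCSA summary does not use it. A patient who enters with raised transaminases and stays above the limit is counted in the treatment percentage just like a patient who crosses the limit for the first time on drug. There is no control arm against which the background rate could be judged.

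This matters most for the liver. The protocol lists liver dysfunction as a disease feature. The rationale for amendment 06 (Protocol 17.2.1) names transient transaminase elevation during dose escalation as an important identified risk. The SAP window includes the parent studies, in which doses were escalated. The liver PCSA table is therefore where pre-existing and new elevations are most likely to meet.

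**Working it through.** The documents state no PCSA rate or baseline prevalence, so there is no figure of the plan's own to reproduce. The check applies the written rules to example values.

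1. **How many criteria are affected (Appendix A, liver and hematology, classed by the low limit where a row has both).** Adults: 5 liver + 10 hematology = 15 rows. Three require a fall from baseline (hemoglobin, hematocrit, platelets), leaving 15 - 3 = 12. Children: 12 applicable rows, since monocytes, basophils and RBC are marked not applicable. Two require a fall (hemoglobin, platelets), leaving 12 - 2 = 10. Liver rows requiring a change: 0 of 5 in either group.

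2. **A pre-existing liver abnormality that improves.** ALT is 3.5 x ULN at baseline and 3.2 x ULN on treatment. PCSA: 3.2 > 3, so it is counted. The first quantifiable dose-limiting toxicity criterion in SAP 2.1.3.1 (DLT1) needs a value above 3 x baseline, here 3 x 3.5 = 10.5 x ULN, so it is not met.

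3. **Low platelets, for contrast.** Baseline 80 GIGA/L. On treatment at 80 the fall is 0%, and at 70 it is (80 - 70)/80 = 12.5%; neither is a PCSA. At 64 it is (80 - 64)/80 = 20%, which is. Stable thrombocytopenia is not counted.

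4. **Pediatric hematocrit.** The limit for ages 2 to under 18 is below 0.32, with no change condition. A child with a stable hematocrit under 0.32 is counted, although the same child's stable hemoglobin would not be.

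5. **A new rise that the other rules do not pick out.** Patient A: ALT goes from 2 to 5.5 x ULN, no symptoms or eosinophilia, bilirubin and alkaline phosphatase (AP) unchanged. Patient B: ALT stable at 5.5 x ULN.
   - PCSA: both exceed the 3 and 5 x ULN steps and neither exceeds 10, so they are counted identically.
   - Shift table (normal/above/below): both read above to above.
   - DLT1 for A: 5.5/2 = 2.75 x baseline, short of 3. DLT2 needs bilirubin or AP above 1.5 x baseline; the ratio is 1. DLT3 has its enzyme conditions met (5.5 > 3 x ULN; 2.75 > 2 x baseline) but needs symptoms or eosinophilia. No DLT is met.

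6. **Size, by assumption.** Let b be the share of patients who exceed a limit at baseline and still exceed it at an on-treatment test. With no drug effect, the expected count is N x b. For b = 10% to 40%:
   - N = 17 (SAP 1.3): 17 x 0.10 = 1.7 to 17 x 0.40 = 6.8.
   - N = 25 (Protocol 11.2): 25 x 0.10 = 2.5 to 25 x 0.40 = 10.

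**The case against.** The strongest reply is that the PCSA table is not read alone. SAP 2.4.7.2 plans observed values, change and percent change from baseline, shifts from baseline, by-patient plots of WBC, ALT, AST and total bilirubin, and separate PCSA listings. DLT1 to DLT3 all carry a comparison with baseline, are listed (2.4.7.1.3) and trigger narratives (2.5). Protocol 10.5.2.1 has laboratory abnormalities that qualify as events of special interest recorded as adverse events, so those larger rises also reach the adverse event tables. With 17 to about 25 patients, a careful reader can trace each patient's baseline. All of this stands, and it limits the harm. It does not change the count itself: patients A and B above remain indistinguishable in every planned incidence table of laboratory limits.

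A reader might infer more than the documents support:

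- **That disease-related low hemoglobin and platelets are miscounted.** They are not, because both criteria require a fall from baseline. They are also the only blood values the protocol ties to ASMD. For WBC and the differential counts no passage names ASMD as a cause; there the point is only that any pre-existing abnormality, whatever its origin, is counted.
- **That a large liver signal could be hidden.** A rise from 2 to 12 x ULN passes the 5 and 10 x ULN steps, which a stable 4 x ULN does not. At 12/2 = 6 x baseline it also meets DLT1.
- **That the plan presents these values as toxicity.** It calls them potentially clinically significant abnormalities, and Protocol 11.6.3 keeps the safety analysis descriptive.
- **That the protocol made its liver stopping rules baseline-relative because baseline values are raised.** It states the rules and gives no reason.

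**Conclusion.** The point holds for the criteria without a change condition: all the liver rows, WBC and the differential counts, and pediatric hematocrit. For these, the stated rule mixes abnormalities present before treatment with those arising on it, and the resulting percentage cannot be read as an incidence of new abnormalities. It does not hold for low hemoglobin, low platelets or adult low hematocrit.

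The size cannot be derived from the documents. The range of 1.7-6.8 of 17, or 2.5-10 of 25, rests on two assumptions: that 10-40% of patients met a limit before treatment, and that they still met it on treatment. The parent studies' liver entry limits, which would help narrow this, are not given. This is a reporting weakness worth correcting and partly mitigated by other outputs. It is not evidence that a safety signal would be missed.

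**What to change.** For the liver tests and the other absolute-limit criteria, report each PCSA limit by baseline status against that same limit: not met, met, or missing. Use the baseline already defined in SAP 2.6.1.

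- **Main line:** numerator and denominator restricted to patients who did not meet the limit at baseline.
- **Second line:** patients who already met it, with the number moving to a higher ALT, AST or bilirubin step. Children have only one bilirubin limit, so the bilirubin step applies to adults.
- **Third line:** patients with no baseline value.

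Under this layout the ALT of 3.5 falling to 3.2 x ULN moves to the second line with no step up. Patient A enters the main line for the 3 and 5 x ULN limits, and patient B stays on the second line. The baseline-relative criteria need no change.

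The cost is one extra classification in tables already planned, with no new data. The drawback is small denominators: among the 5 adults from DFI13412, one patient is at least 1/5 = 20%. Counts with their denominators should therefore be shown beside any percentage.
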